7.0 Protocol Treatment

7.1 Preoperative Evaluation Imaging

All patients must have a bilateral diagnostic mammogram prior to registration on this trial (a bilateral breast MRI is optional). Any additional breast imaging modality (i.e., breast sonography, MRI, PEM, BSGI, MBI, breast tomosynthesis or other imaging modality) performed should also be documented and reports and images submitted to IROC Rhode Island (QARC). These reports should also be submitted to the study QAS/Data Manager listed on the Protocol Resources page using the Report Submission Form in Rave. Sites who are not able to scan and attach the reports should contact the QAS/Data Manager for further instructions.

7.11 Bilateral Mammography

The diagnostic mammography should consist of the standard craniocaudal (CC) and mediolateral oblique (MLO) views. Additional spot compression views for mass lesion and magnification views for micro calcifications should be performed, as requested by the interpreting radiologist. The mammographic reports should follow the standardized terminology of the American College of Radiology Breast Imaging Reporting and Data System (BI-RADS ®), in addition to size measurement of the suspicious finding and its distance from the nipple (D'Orsi, 2003). This is part of the data collection forms (lesion size, distance from the nipple and o'clock position in the breast.) Digital mammography is preferred over conventional mammography. All **diagnostic mammogram** images, including images of the computer-aided diagnosis (CAD), and the reports must be submitted to IROC Rhode Island (QARC) for central review. These reports also should be submitted to the study QAS/Data Manager listed on the Protocol Resources Page using the Report Submission Form in Rave. If full field breast tomosynthesis is performed, then the images and report are requested for submission. Sites who are not able to scan and attach the reports should contact the QAS/Data Manager for further instructions.

7.12 Bilateral Breast Magnetic Resonance Imaging (Optional)

MRI requirements described in the Clinical Imaging Guide from the American College of Radiology Accreditation program are highly recommended to ensure adequate coverage of the entire breast and axilla.

[http://www.acr.org/accreditation/Breast-MRI/qc_forms/Clinical-Image-Quality-Guide.aspx. Accessed November 15, 2010.]

The minimum equipment requirements include:

- Dedicated bilateral breast coil.
- Capability of simultaneous bilateral imaging.

- Equipment to perform mammographic correlation, directed breast ultrasound, and MRI-guided intervention, or create a referral arrangement with a cooperative facility for these services.
- Slice thickness of 3 millimeters or less, no gap, in-plane pixel of 1 millimeter or less, and a dynamic series with pre-contrast T1-weighted images followed by at least three post-contrast T1-weighted images within 8 minutes of completion of IV contrast injection.

All reporting should have final BI-RADS assessment per ACR BI-RADS-MRI (Ikeda *et al.*, 2003).

The MR imaging protocol should contain the minimum sequences recommended by the American College of Radiology listed below:

- T2 images with fat saturation (4-5 millimeter slice thickness),
- Pre-contrast T1 gradient echo images with fat saturation (\leq 2 millimeter slice thickness, no gap),
- Post-contrast T1 gradient echo images with fat saturation (\leq 2 millimeter slice thickness, no gap) with at least two sequences with images obtained immediately after intravenous injection of gadolinium (at T0) and at 3-4 minutes after intravenous injection of gadolinium.

All images including those from the use of computer-aided diagnosis (CAD), pharmacokinetic or other parametric mapping along with reports must be submitted to IROC Rhode Island (QARC) for central review. MRI reports should also be sent to IROC Rhode Island (QARC) and to the study QAS/Data Manager listed on the Protocol Resources Page using the Report Submission Form in Rave. Sites who are not able to scan and attach the reports should contact the QAS/Data Manager for further instructions.

7.13 Additional Imaging

If any other imaging modality is performed (such as whole breast ultrasound, breast specific gamma imaging [BSGI], molecular breast imaging [MBI], positron emission mammography [PEM] or breast tomosynthesis), please submit these images and reports to IROC Rhode Island (QARC) for central review. Reports should also be submitted to the study QAS/Data Manager listed on the Protocol Resources Page using the Report Submission Form in Rave. Submit these images and reports regardless of whether they detected all sites of MIBC or not. Sites who are not able to scan and attach the reports should contact the QAS/Data Manager for further instructions.

7.14 Image-Guided Biopsy and Specimen Radiographs

All suspicious imaging abnormalities (BI-RADS® 4 or 5 lesions) amendable to biopsy should undergo imaged guided biopsy, preferably with clip marker placement at the time of biopsy. Fine needle aspiration or core biopsy is permissible, however, a minimum of one lesion must have core biopsy documenting invasive disease. Submit images of biopsies of each suspicious

lesion. Submit procedure reports and pathology reports from each site biopsy. If specimen radiographs are performed at the time of the surgery, please submit these images as well. The means of diagnosis (percutaneous core or excisional/incisional) will be documented and tracked.

Submit images and the reports from all image-guided biopsies performed (mammogram, ultrasound, MRI, breast-specific gamma imaging (BSGI), PEM, and/or tomosynthesis guided biopsies) with the procedure report and pathology report from the biopsy.

7.15 Central Radiologic Review

The mammograms and any other adjuvant imaging performed will be centrally reviewed using a process that is blinded to the results of the surgery and pathology. If mammograms, breast MRI and other imaging studies were not performed or will not be submitted for technical reasons, notify IROC Rhode Island (QARC) by email at [REDACTED] Digital files must be in DICOM format and include all image attributes. These files can be submitted electronically via sFTP. Details for obtaining an sFTP account and submission instructions can be found at [REDACTED] Follow the link labeled digital data. Alternatively, if sFTP is not feasible, the imaging may be burned to a CD and mailed to IROC RI (QARC) at the address below. Multiple studies for the same patient may be submitted on one CD; however, please submit only one patient per CD. Contact IROC RI (QARC) with questions or for additional information.

7.16 Image Submission

Submit required images as follows:

- Diagnostic mammogram images and report
- Diagnostic breast MRI images and reports (if MRI performed)
- Images by any additional imaging (by any modality) and reports
- Image guided biopsy images, procedure report **and** pathology report from the biopsy

Complete and include an Image Submission Checklist with submission to IROC Rhode Island (QARC); checklists may be downloaded from the IROC Rhode Island (QARC) website [REDACTED]

Send to IROC Rhode Island (QARC) at the address listed on the Protocol Resources page of the protocol.

7.2 Surgery

Patients undergoing breast conserving therapy (BCT) for multiple ipsilateral breast cancers should have all lesions resected to negative margins, either using one lumpectomy or two/three separate lumpectomy incisions at the discretion of the surgeon. Lumpectomy specimens must be oriented and submitted for pathological assessment of margins. Intra-operative confirmation of tumor resection is recommended with intra-

operative specimen radiograph. All sites of biopsy proven malignancy (DCIS or invasive breast cancer) and atypia (atypical ductal hyperplasia (ADH), atypical lobular hyperplasia (ALH) and flat epithelial atypia (FEA)) should be resected at time of surgery.

Primary tumor bed will be defined as the area of invasive and/or DCIS and include nearby small satellite nodules within 1 centimeter of the index lesion.

Each tumor must be resected to negative margins (no tumor at ink).

Re-excision should be done to achieve negative margins as needed. Patients with persistent positive margins should be converted to mastectomy or go off study. For patients who convert to mastectomy within one year of initial surgery, see Section 13.2.

Where possible, surgical clips must be placed to outline the surgical bed for all patients. For patients where an oncoplastic approach to the surgical resection is undertaken, clips must be placed to outline the surgical bed. For the oncoplastic patients, the tissue rearrangement must be clearly documented in the operative report to facilitate radiation planning. Oncoplastic tissue rearrangement by the breast surgeon or plastic surgeon is permitted. Planned autologous tissue flaps (such as latissimus flap, etc.) or implants are not permitted.

Axillary staging is required for all invasive breast cancers with sentinel lymph node (SLN) surgery and/or axillary lymph node dissection (ALND). Completion ALND in the setting of one or two positive sentinel lymph nodes is at the discretion of the treating surgeon. Surgeons are encouraged to perform ALND for patients with three or more positive sentinel nodes or evidence of extra nodal extension in any of the positive sentinel nodes. The status of the axilla will be documented in the trial data collection.

7.3 Pathology

Margin assessment of each lumpectomy specimen is required. For this study negative margin is defined as no tumor at ink. The size of the closest margin should be measured and reported for each lesion. The anterior and posterior margins are excluded from this restriction if the fascia and/or skin are taken.

When 2 or more lesions are excised en bloc, surgical pathology review is required to assess whether the lesions are separate foci of cancer separated by 2 cm or more of healthy breast tissue.

In consenting patients, tissue from each site of disease within the breast will be submitted for tissue banking and correlative science section. Tissue from axillary lymph nodes (sentinel lymph nodes and/or axillary lymph node dissection dependent on case) will also be collected for correlative science evaluation.

Patient may remain on study if, upon pathological assessment, two or three lesions identified on pre-operative imaging represent one contiguous lesion.

7.4 Cosmesis

Following surgery, patients will complete questionnaire booklets at the following time points: 5 to 30 days following final surgery (initial post-operative visit); every six months (\pm 1 month) for the first 2 years following completion of WBI; then yearly (\pm 2 months) for the next 3 years following completion of WBI to assess cosmetic outcome. The

patient's surgeon will complete the surgeon questionnaire 5 to 30 days following final surgery (initial post-operative visit) to assess cosmetic outcome. Patients registered after surgery will still complete the questionnaire at the timepoints feasible, based on the timing of their registration.

7.5 Adjuvant Therapy

The use of adjuvant chemotherapy or endocrine therapy will be at the discretion of the treating medical oncologist at the individual institutions based on tumor characteristics. Patients being treated with adjuvant therapy should be treated within 12 weeks following surgery. It is recommended that patients with hormone responsive tumors receive tamoxifen or an aromatase inhibitor. It is recommended that patients with Her2 positive tumors receiving adjuvant chemotherapy receive targeted anti-Her2 therapy.

7.6 Adjuvant Whole Breast Irradiation (WBI)

Patients receiving BCT should receive adjuvant whole breast radiation with a boost to the lumpectomy bed of each site of disease. The boost will be limited to two quadrants of the breast only. **Note:** Patients who cannot or do not receive boost radiation are ineligible and must discontinue the study. The end of study information should be collected and the patient referred to clinical care. Addition of nodal radiation fields will be at the discretion of the treating radiation oncologist.

Patients may receive WBI at an institution other than the enrolling institution. Note that the enrolling institution is responsible for the correct performance of WBI at the other institution and the reporting of all study data. The institution performing WBI must follow all requirements for WBI listed in the protocol, including regulatory requirements such as submission of an RTFI form to CTSU and submission of treatment plans to IROC Rhode Island (QARC).

7.61 Treatment Planning/Delivery

- 7.611 Three-dimensional CT-based treatment planning is required.
- 7.612 Heterogeneity corrections are required.
- 7.613a Intensity modulated radiotherapy (IMRT) with inverse planning is allowed.
- 7.613b Breath hold technique is allowed
- 7.614 Optimization with forward planning is allowed.
- 7.615 Linear accelerators with minimal photon energies of 6MV and electron energies of 6eMEV-20eMEV are required.
- 7.616 Either electrons or photons may be used for boost treatment.
- 7.617 Boost treatment to each lumpectomy cavity is required.
Note: Patients who cannot or do not receive a boost are ineligible and must discontinue the study. The end of study information should be collected and the patient referred to clinical care.
- 7.618 Boost with intraoperative radiotherapy or HDR brachytherapy is not allowed.
- 7.619 Hypofractionation is not allowed.

7.62 Timing of WBI for Patients Receiving Adjuvant Chemotherapy

- 7.621 For patients receiving adjuvant cytotoxic chemotherapy, radiation treatment planning and cavity assessment is performed after completion of chemotherapy. WBI should be initiated \leq 8 weeks after the last dose of cytotoxic chemotherapy. For patients receiving trastuzumab as part of their therapy the trastuzumab can continue during WBI.
- 7.622 Patients not meeting the dose constraints by 8 weeks after completion of adjuvant cytotoxic chemotherapy should discontinue protocol therapy and are recommended to undergo mastectomy (see Section 13.2).

7.63 Timing of WBI for Patients Not Receiving Adjuvant Chemotherapy

- 7.631 For patients not receiving adjuvant cytotoxic chemotherapy, radiation treatment planning is to be performed within 6 weeks of lumpectomy (or final operation for re-excision of margins) to determine if the volume of breast tissue receiving 60 Gy is less than or equal to 50% of Breast PTV Eval (see below). If the dose constraint is met, WBI should be initiated by no later than 10 weeks following lumpectomy or re-excision of margins, provided surgical incisions have healed adequately.
- 7.632 WBI can be carried out concurrently with hormonal therapy; hormonal therapy can be started at any time at the discretion of the treating physician.
- 7.633 If the dose constraint is not met, patients will be re-scanned no later than 10 weeks after lumpectomy (or final margin re-excision) to allow for cavity shrinkage.
- 7.634 If the dose constraint is not met within 10 weeks from the last surgery, these patients will discontinue protocol therapy and are recommended to undergo mastectomy, see Section 13.2.
- 7.365 For patients who are re-scanned at 10 weeks and the dose constraint is met at that time, radiation should start no later than 12 weeks post-surgery.

7.64 Patient Positioning, Immobilization and Imaging

- 7.641 Simulation CT and treatment delivery should be performed according to institutional standards.
- 7.642 Radio-opaque markers placed on the lumpectomy incisions, around the palpable breast tissue, and at the borders of the “clinical” tangent fields are often helpful.
- 7.643 Immobilization using alpha cradle, vac-loc, or breast boards is highly recommended to ensure reproducibility. Prone position is permitted.

7.644 The CT should extend cephalad to start at or above the mandible and extend sufficiently caudally (or inferiorly) to the inframammary fold to encompass the entire lung volume. A CT scan image thickness of ≤ 0.5 cm should be employed.

7.645 External skin localizing marks, which may include permanent tattoos, are recommended for radiation daily localization and set-up accuracy.

7.646 The patient may be re-positioned for boost delivery at the discretion of the treating physician.

7.65 Target Volumes

The definitions for the CTV, PTV and normal structures used in this protocol generally conform to the RTOG-endorsed consensus guidelines for delineation of target and normal structures for breast cancer

7.651 Breast volumes

7.6511 Breast CTV

Includes the palpable breast tissue demarcated with radio-opaque markers at CT simulation, the apparent CT glandular breast tissue visualized by CT, consensus definitions of anatomical borders, and the Lumpectomy CTV from the breast cancer atlas. The breast CTV is limited anteriorly within 5 mm from the skin and posteriorly to the anterior surface of the pectoralis, serratus anterior muscle excluding chest wall, boney thorax, and lung. In general, the pectoralis and/or serratus anterior muscles are excluded from the breast CTV unless clinically warranted by the patient's pathology. The breast CTV should generally follow consensus guidelines

7.6512 Breast PTV

Breast CTV + 7 mm 3D expansion (exclude heart and do not cross midline).

7.6513 Breast PTV Eval

Since a substantial part of the Breast PTV often extends outside the patient, the Breast PTV is then copied to a Breast PTV Eval which is edited. This breast PTV Eval is limited anteriorly to exclude the part outside the patient and the first 5 mm of tissue under the skin (in order to remove most of the build-up region for the DVH analysis) and posteriorly is limited to no deeper than the anterior surface of the ribs (excludes boney thorax and lung). This Breast PTV Eval is the structure used for DVH constraints and analysis. This Breast PTV Eval cannot be used for beam aperture generation.

7.652 Lumpectomy volume

7.6521 Lumpectomy GTV

Contour using all available clinical and radiographic information including the excision cavity volume, architectural distortion, lumpectomy scar, seroma and/or extent of surgical clips.

Patients without a clearly identifiable lumpectomy bed are not eligible for protocol participation.

7.6522 Lumpectomy CTV

Lumpectomy GTV + 1 cm 3D expansion. Limit the CTV posteriorly at anterior surface of the pectoralis major and anterolaterally 5 mm from skin and should not cross midline. In general, the pectoralis and/or serratus anterior muscles are excluded from the lumpectomy CTV unless clinically warranted by the patient's pathology.

7.6523 Lumpectomy PTV

Lumpectomy CTV + 3-5 mm 3D expansion (excludes heart).

7.6524 Lumpectomy PTV Eval

Since a substantial part of the Lumpectomy PTV often extends outside the patient (especially for superficial cavities), the Lumpectomy PTV is then copied to a Lumpectomy PTV Eval which is edited. This Lumpectomy PTV Eval is limited to exclude the part outside the ipsilateral breast and the first 5 mm of tissue under the skin (in order to remove most of the build-up region for the DVH analysis) and excluding the Lumpectomy PTV expansion beyond the posterior extent of breast tissue (chest wall, pectoralis muscles and lung) when pertinent. The lumpectomy PTV should not cross midline. This Lumpectomy PTV Eval is the structure used for DVH constraints and analysis. This Lumpectomy PTV Eval cannot be used for beam aperture generation.

7.653 Normal Tissues

7.6531 Ipsilateral lung.

This may be contoured with auto-segmentation with manual verification.

7.6532 Contralateral lung.

This may be contoured with auto-segmentation with manual verification.

7.6533 Heart.

The heart should be contoured beginning just inferior to the level in which the pulmonary trunk branches into the left and right pulmonary arteries (PA). Above the PA, none of the 4 chambers are present. All the mediastinal tissue below this level should be contoured, including the great vessels (ascending and descending aorta, inferior vena cava) and defined as "heart". The heart should be contoured on every contiguous slice thereafter to its inferior most extent near the diaphragm. If one can identify the

esophagus, this structure should be excluded from the heart. One need not include pericardial fat, if present. Contouring along the pericardium itself, when visible, is appropriate.

7.66 Target Dose Fractionation and Dose Prescription

7.661 Whole breast

46-50 Gy in 2 Gy daily fractions or 45-50.4 Gy in 1.8 Gy daily fractions, 5 days a week.

Per protocol: $\geq 95\%$ of the breast PTV Eval will receive $\geq 95\%$ of the prescribed dose. Maximal point dose will be $\leq 115\%$ of the prescribed dose, not including the boost dose.

Acceptable Variation: $\geq 90\%$ of the breast PTV Eval will receive $\geq 90\%$ of the prescribed dose. Maximal point dose will be $\leq 120\%$ of the prescribed dose, not including the boost dose.

7.662 Boost

10-16 Gy in 2 Gy daily fractions, 5 days a week (10 Gy for those receiving 50-50.4 Gy to the whole breast, 14 Gy for those receiving 46 Gy to the whole breast, 16 Gy for those receiving 45 Gy to the whole breast).

Per protocol: $\geq 90\%$ of the lumpectomy PTV Eval will receive $\geq 90\%$ of the prescribed dose. Maximal point dose will be $\leq 115\%$ of the boost prescription dose.

7.663 Accumulative Dose (Whole Breast + Boost)

Per protocol: No more than 50 % of Breast PTV Eval will receive more than 60 Gy.

Acceptable Variation: No more than 60 % of Breast PTV Eval will receive more than 60 Gy.

Every effort should be made to keep no more than 50% of Breast PTV Eval receiving more than 60 Gy, including using 3mm margin for expansion from Lumpectomy CTV to Lumpectomy PTV, and allowing minimum coverage of 90% of the lumpectomy PTV Eval receiving 90% of the prescribed dose.

7.67 Nodal Irradiation

The addition of nodal irradiation is at the discretion of the treating radiation oncologist.

7.671 For those patients with 1-2 positive sentinel lymph nodes (SLNs) not undergoing axillary lymph node dissection, the use of either standard tangent fields or “high tangent fields” covering part or all level II axillary LNs is permitted and is at the discretion of the treating radiation oncologist.

7.672 For those patients with $\geq 3+$ SLNs undergoing axillary lymph node dissection, regional nodal irradiation is encouraged, especially in those

with extra capsular extension, nodal ratio > 20 %, high grade disease, and LVSI. Coverage of supraclavicular fossa and high axillary lymph node regions are recommended. Coverage of the internal mammary nodes is at the discretion of the radiation oncologist.

- 7.673 For those patients with ≥ 3 positive SLNs not undergoing axillary lymph node dissection, regional nodal irradiation is required.
- 7.674 If regional lymph nodes are treated, contouring of regional lymph nodes per the RTOG breast contouring atlas is required.
- 7.675 Nodal irradiation dose
Undissected axilla, supraclavicular nodes, internal mammary nodes: 46-50 Gy in 2 Gy daily fractions or 50.4 Gy in 1.8 Gy daily fractions, 5 days a week.

7.68 Dose Limitation for Normal Tissues

- 7.681 Ipsilateral Lung
Per Protocol: $\leq 30\%$ of the ipsilateral lung should receive ≥ 20 Gy
Variation Acceptable: $\leq 35\%$ of the ipsilateral lung should receive ≥ 20 Gy
- 7.682 Contralateral Lung
Per Protocol: $\leq 10\%$ of the contralateral lung should receive 5 Gy or more
Variation Acceptable: $\leq 15\%$ of the contralateral lung should receive 5 Gy or more
- 7.683 Heart
Per Protocol: $\leq 5\%$ of the whole heart should receive ≥ 25 Gy for left-sided breast cancers, and 0% of the heart should receive ≥ 25 Gy for right-sided breast cancers
Variation Acceptable: $\leq 5\%$ of the whole heart should receive ≥ 30 Gy for left-sided breast cancers, and 0% of the heart should receive ≥ 30 Gy for right-sided breast cancers
Per Protocol: Mean heart dose should be ≤ 400 cGy
Variation Acceptable: ≤ 500 cGy. Every attempt should be made to make the cardiac exposure to radiation as low as possible

7.69a Data Submission

Submission of treatment plans in digital format (either DICOM RT or RTOG format) is required. Digital data must include CT scan structures, dose, and plan files. Submission may be either by sFTP or CD. Instructions for data submission are available on the IROC Rhode Island (QARC) website at [REDACTED] Any items on the list below that are not part of the digital submission may be submitted as screen captures along with the digital data.

- 7.69a1 Prior to the Start of Radiotherapy
The following data should be submitted prior to the start of radiotherapy:

- a. Treatment Planning System Output
 - 1. RT treatment plan including CT, structures, dose, and plan files. These items are included in the digital plan.
 - 2. Dose volume histograms (DVH) of target volumes, ipsilateral and contralateral lung and heart. DVH's are included in the digital plan.
 - 3. Digitally reconstructed radiographs (DRR) for each treatment field.
 - 4. Treatment planning system summary report that includes the monitor unit calculations, beam parameters, calculation algorithm, and volume of interest dose statistics.

- b. Supportive Data
 - 1. Prescription Sheet for Entire Treatment
- c. Forms
 - 1. RT-1 Dosimetry Summary Form
This form is available on the IROC Rhode Island (QARC) website at [REDACTED]

7.69a2 Within One Week of the Completion of Radiotherapy

The following data should be submitted within one week of the completion of radiotherapy:

- a. The RT-2 Radiotherapy Total Dose Record Form
This form is available on the IROC Rhode Island (QARC) website at [REDACTED]
- b. A copy of the patient's radiotherapy record including prescription, and the daily and cumulative doses to all required areas, critical organ, and reference points
- c. Documentation listed above showing any modifications from original submission.

7.69a3 Supportive data and forms may be included with the transmission of the digital RT data via sFTP or submitted separately via e-mail ([REDACTED]) or mailed to IROC Rhode Island (QARC) at the address listed on the Protocol Resources page of the protocol.

7.69a4 Questions regarding the dose calculations or documentation should be directed to the protocol dosimetrist at IROC Rhode Island (QARC) at the address, email and telephone number listed on the Protocol Resources page of the protocol.

7.69b Quality Assurance

7.69b1 Whole Breast Dose

Variation Acceptable: < 95% of the Breast PTV Eval receives < 95% of the whole breast prescription dose (not including boost dose)

Deviation Unacceptable: < 90% of the Breast PTV Eval receives < 90% of the whole breast prescription dose (not including the boost dose)

Deviation Unacceptable: Maximal point dose is > 120% of the whole breast prescribed dose (not including the boost dose)

7.69b2 Boost Volume Coverage

Deviation Unacceptable: < 90% of the lumpectomy PTV Eval receives < 90% of the boost prescription dose.

7.69b3 Accumulative Breast Dose

Variation Acceptable: Between 50% and 60% of Breast PTV Eval receives more than 60Gy
Deviation Unacceptable: More than 60 % of Breast PTV Eval receives more than 60 Gy.

7.69b4 Volume

Deviation Unacceptable: Whole breast or boost volumes incorrectly defined as deemed by study co-PI.

7.69b5 Critical Organ

The dose to lung or heart-exceeds the protocol's limits specified in Section 7.68

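### The coverage lines in 7.69b1 and 7.69b2 reverse both inequalities, so as written they contradict the coverage criteria in 7.661 and 7.662

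*Combined protocol and SAP*

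**What the plan says.** The target-dose sections state coverage positively, as a share of the volume at or above a dose level.

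- 7.661, whole breast. The pattern is that a minimum share "of the breast PTV Eval will receive" at least a given percentage of the prescribed dose. The pair is 95% and 95% for per protocol, and 90% and 90% for an acceptable variation.
- 7.662, boost. Per protocol is at least 90% of the Lumpectomy PTV Eval receiving at least 90% of the prescribed dose. No acceptable variation in coverage is given.

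The quality assurance section uses the same percentages, with a less-than sign in both positions.

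- 7.69b1, Variation Acceptable: "< 95% of the Breast PTV Eval receives < 95% of the whole breast prescription dose".
- 7.69b1, Deviation Unacceptable: "< 90% of the Breast PTV Eval receives < 90% of the whole breast prescription dose".
- 7.69b2, Deviation Unacceptable: "< 90% of the lumpectomy PTV Eval receives < 90% of the boost prescription dose".

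Other lines in 7.69b do not have this problem. 7.69b3 classes a plan as unacceptable when "More than 60 % of Breast PTV Eval receives more than 60 Gy", which agrees with 7.663. The whole-breast maximal point dose line in 7.69b1 (above 120%) agrees with 7.661.

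**The concern.** A deviation category should contain the plans that fail the coverage criterion. The opposite of at least 90% of the volume receiving at least 90% of the dose is less than 90% of the volume receiving at least 90% of the dose. Only the volume inequality changes direction; the dose inequality stays. The three coverage lines change both, and so describe a different set of plans.

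At stake is the written standard for central review of the radiation. The test schedules (4.1 footnote 15, 4.2 footnote 6) require the radiation plan and treatment summary to be submitted for that review. 7.69b is the section that names the categories. Section 7.6 lets patients be irradiated away from the enrolling institution, which stays responsible for correct performance, so more than one site may have to work from this text. If a report later states how many plans were per protocol or deviant on coverage, the answer depends on whether 7.66 or 7.69b was applied.

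**Working it through.** No sample size, power or alpha figure is involved, and the plan gives no figure to reproduce. The check is logical.

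**Notation.** V95 and V90 are the percentages of the PTV Eval receiving at least 95% and at least 90% of the prescribed dose. The percentage receiving less than those levels is 100 − V95 and 100 − V90.

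**Criteria in 7.661 and 7.662.**
- Whole breast, per protocol: V95 ≥ 95.
- Whole breast, acceptable variation: V90 ≥ 90.
- Boost, per protocol: V90 ≥ 90, on the Lumpectomy PTV Eval.

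**Lines in 7.69b1 and 7.69b2, read literally.**
- Variation Acceptable: 100 − V95 < 95, that is V95 > 5.
- Deviation Unacceptable, whole breast: 100 − V90 < 90, that is V90 > 10.
- Deviation Unacceptable, boost: the same, V90 > 10.

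The failure of V90 ≥ 90 is V90 < 90, not V90 > 10.

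**Whole-breast test plans (coverage only).**

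| V95 | V90 | 7.661 | 7.69b1 Variation, literal | 7.69b1 Deviation, literal |
|---|---|---|---|---|
| 100 | 100 | per protocol | yes (0 < 95) | yes (0 < 90) |
| 95 | 98 | per protocol | yes (5 < 95) | yes (2 < 90) |
| 85 | 90 | acceptable variation | yes (15 < 95) | yes (10 < 90) |
| 60 | 80 | meets neither | yes (40 < 95) | yes (20 < 90) |
| 5 | 50 | meets neither | no (95 < 95 is false) | yes (50 < 90) |
| 5 | 10 | meets neither | no (95 < 95 is false) | no (90 < 90 is false) |
| 0 | 0 | meets neither | no (100 < 95 is false) | no (100 < 90 is false) |

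The deviation column depends on V90 alone, so it also gives the 7.69b2 result for a boost with the same V90.

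**Whole range.** Over the integer values V90 = 0 to 100:
- All 11 values that satisfy V90 ≥ 90 (90 to 100) are flagged as unacceptable.
- Of the 90 values below 90, 79 (11 to 89) are flagged, in agreement with 7.661 and 7.662.
- The remaining 11 (0 to 10) are not flagged.

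This grid shows where the rule goes wrong. It is not a distribution of patients.

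**Check on the cause.** If the dose inequality is put back to at least, and a variation is also required to have V90 ≥ 90, the categories become V90 < 90 for a deviation and V95 < 95 with V90 ≥ 90 for a variation. All the test plans then fall where 7.661 and 7.662 put them. The second less-than sign, together with the missing lower limit on the variation line, accounts for the contradiction. This uses only the document's own thresholds.

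**The case against.** The best reply is that this is a slip of wording that no competent dosimetry reviewer would follow. The percentages in 7.69b1 and 7.69b2 are those of 7.661 and 7.662. Those sections run in a sensible direction, as do the neighbouring lines of 7.69b. The literal reading puts one plan in two categories and lets the worst plans through. Section 7.69a4 sends dosimetry questions to the protocol dosimetrist. All of this stands, and it makes literal use unlikely. It does not make the written rule correct, and the text does not show which wording was applied.

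A second reply is that nothing in the statistical plan uses the categories. This also stands. The primary analysis set (16.2, 16.61) turns on eligibility, margins, conversion to mastectomy and, in 16.61, a single contiguous lesion. Discontinuation and ineligibility (7.6, 7.622, 7.634, 13.2, 13.3, 13.5) turn on matters such as receipt of the boost, the dose constraint and the entry criteria. Sections 16.5 and 16.6 plan no deviation rate, no radiation per-protocol set and no sensitivity analysis by QA category.

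Three stronger readings are therefore tempting but unsupported.
- **Nearly all irradiated patients were misclassified.** That needs reviewers to have applied the literal text. The documents do not show that they did, and do not describe how scores are assigned or recorded.
- **A deviation rate would be the reverse of delivered quality.** Plans with V90 above 10% and below 90% are flagged on either reading, so the literal rule is not a mirror image. The plan specifies no such rate.
- **The local recurrence estimate is compromised.** No rule carries these categories into that estimate, and the documents do not say how far coverage determines local control.

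Any mis-scoring could also be repaired: 7.69a requires digital plans with structures, dose and dose-volume histograms.

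**Conclusion.** The inconsistency is real and the three lines are wrong as written. It is a minor point. On the text alone the logic is certain: no reading of two less-than signs gives the complement of the 7.661 and 7.662 criteria. What is uncertain is the practical effect. If central review read for intent, there is none beyond an ambiguous standard. If any plans were scored literally, every one with acceptable coverage was labelled an unacceptable deviation, and any with V90 at or below 10% passed unflagged. In either case the damage stops at the central QA classification and statements of radiation compliance drawn from it.

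The conclusion assumes that the inequality signs in the extracted text are those of the protocol. The same pattern in three separate lines, beside correctly directed ones, gives no sign of an extraction fault.

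**What to change.** Reconcile 7.69b1 and 7.69b2 with 7.661 and 7.662 so that each plan falls into exactly one coverage category, and the same one under both sections. Whatever thresholds the sponsor confirms, the deviation line should be the logical complement of the coverage criterion. The whole-breast variation line should exclude plans that are already per protocol or already deviations. Which coverage thresholds are clinically right is for the sponsor and is not addressed here.

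Ask the QA center to confirm in writing which wording was applied to plans already scored. If the literal wording was used for any of them, re-derive those categories from the submitted dose-volume histograms. Any later report of radiation compliance should say which definition it uses.

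The cost is a wording amendment and one query, with re-scoring from stored data only if the query shows a need. Sample size, endpoints and analysis sets are untouched.
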